Study Title: “Best Practice Alert for Opioid Prescribing” NCT04446975

09/01/2022

Study Protocol and Statistical Analysis Plan

The study is a randomized multiple crossover cluster trial to evaluate a real-time best practice alert embedded into the electronic health record. Our clusters are an academic medical center and three community hospitals, all part of the University of Colorado Health system, which serves both inner-city and rural populations. Primary study subjects are credentialed prescribing providers at each site. Eligible secondary study subjects are postsurgical hospital inpatients who are hospitalized at least one night prior to discharge. There are no exclusion criteria for the prescribing providers. The exclusion criteria for eligible patients is being less than 18 years of age.

During the eight-week periods when prescriber alerts are active, providers that attempt to prescribe higher-than-optimal doses are automatically notified on the order screen with a suggestion for a recommended dose. In the subsequent eight-week period, there is no best practice alert available to trigger. The four hospitals are randomized to the alert starting configuration (ON vs. OFF) in alternating clusters between best practice alert ON and OFF conditions for four eight-week periods, each separated by a four-week washout interval to minimize learning and augment masking. Randomization is implemented, so investigators and data analysts remain masked to the condition designation. While providers are exposed to the alerts during active periods if their prescription triggers a best practice alert, the schedule was not shared with providers or patients.

Baseline characteristics balance is assessed using absolute standardized difference calculated as the difference in means or proportions divided by the pooled standard deviation. An absolute standardized difference > 0.1 was considered to indicate an imbalance. The analysis is conducted at the individual patient level using a modified intention-to-treat strategy. The effect of the best practice alert on opioid prescription at discharge is evaluated using a linear regression model.

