We determined that it would be feasible to recruit 1,500 patients per cluster period across four hospitals for four time periods. Although we considered a 33.3% reduction of prescribed opioids a clinically meaningful reduction for prescriptions “exposed” to the best practice alert, we utilized a smaller effect size (11.1% reduction) for the power analysis to incorporate the average effect across all patients. We estimated that the trial would have $>99\%$ power to detect a ratio of geometric means of 0.89 (ON/OFF) for the amount of prescribed opioids or a difference of -0.12 (ON – OFF) on the log-scale, at the 0.05 significance level.

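### The planned patient-level linear regression names no hospital or period terms and no clustered variance; fix both before unmasking

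*Combined protocol and SAP*

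**What the plan says.** All of this comes from the combined protocol and SAP, which has no numbered sections.

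- Design paragraphs: "Our clusters are an academic medical center and three community hospitals". Each hospital is randomized to start with the alert on or off and then alternates over "four eight-week periods, each separated by a four-week washout interval". The text does not say how many hospitals start in each condition. Analysts are masked to condition.
- Analysis paragraph: "The analysis is conducted at the individual patient level using a modified intention-to-treat strategy". Then: "The effect of the best practice alert on opioid prescription at discharge is evaluated using a linear regression model". The paragraph lists no covariate, random effect or variance method. Just before this, a balance rule is given ("An absolute standardized difference > 0.1 was considered to indicate an imbalance"), with no stated consequence for the model.
- Power paragraph: "We determined that it would be feasible to recruit 1,500 patients per cluster period across four hospitals for four time periods". It claims more than 99% "power to detect a ratio of geometric means of 0.89 (ON/OFF) for the amount of prescribed opioids or a difference of -0.12" on the log scale, at the 0.05 level. It gives no SD, intracluster correlation or model terms.

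**The concern.** The model sentence does not carry the design into the analysis. There are 16 hospital-periods, and the alert is switched on or off for a whole hospital-period at a time. A regression of the outcome on condition alone makes two choices by default.

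First, it leaves hospital and calendar differences in the contrast whenever volumes or starts are unbalanced. Second, it computes the standard error as if every patient were an independent unit. The first adds noise to the estimate. The second can make the test reject too often.

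Because the terms are open, they could also be settled after results have been seen. Masking of the analysts limits that risk but does not specify a model.

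**Working it through.** **Inputs from the plan.** 4 hospitals, 4 periods, difference -0.12, level 0.05 (two-sided assumed). The calendar span is 4 × 8 + 3 × 4 = 44 weeks. The 1,500 figure can mean 1,500 per period over all hospitals (375 per hospital-period, 6,000 in total) or 1,500 per hospital-period (24,000 in total), so I show both.

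**Inputs I assume.** Log-scale SD 1, volumes, trend, intracluster correlation (ICC) and cluster autocorrelation (CAC). The plan gives none of these.

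**1. The plan's own figure.** Power of 99% for 0.12 needs SE ≤ 0.12/(1.960 + 2.326) = 0.0280. With independent patients, SE = SD × √(2/n), where n is the number per condition. That allows SD up to 1.08 with 3,000 per condition and up to 2.17 with 12,000. The claim cannot be reproduced without the SD, but it is attainable as an independent-patient calculation.

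**2. Calendar trend in the plain contrast.** A hospital starting ON has mean period 2 when ON (periods 1, 3) and 3 when OFF (periods 2, 4). A hospital starting OFF has the reverse. With a trend of b per period and volumes stable over time, the shift is b × (share of patients in OFF-start hospitals − share in ON-start hospitals). With equal hospitals and 2:2 starts it is zero. With b = -0.05 and volumes 750/350/250/150 (1,500 per period), its absolute size for the three 2:2 pairings is:

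- 750+350 against 250+150: 0.05 × 700/1500 = 0.023, or 19% of 0.12
- 750+250 against 350+150: 0.05 × 500/1500 = 0.017, or 14%
- 750+150 against 350+250: 0.05 × 300/1500 = 0.010, or 8%

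The sign depends on which pair starts ON, so it averages to zero over the randomization. In the first pairing, with 6,000 patients and CAC 1, the plain test rejects a true null in about 14% of trials. With hospital and period terms the shift is 0 and rejection is 5%.

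**3. Standard error.** With total variance 1, m patients per hospital-period and eight hospital-periods per condition:

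- true SE = √{[ICC(1 − CAC) + (1 − ICC)/m]/4}
- plain-regression SE ≈ √(4/N), which is 0.0258 for 6,000 and 0.0129 for 24,000
- rejection of a true null ≈ 2Φ(−1.96 × plain SE/true SE)

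Example: ICC 0.02, CAC 0.9, m = 375 gives √[(0.0020 + 0.0026)/4] = 0.0340. Then 1.96 × 0.0258/0.0340 = 1.49, so rejection is 14%.

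| Patients | ICC / CAC | True SE | Plain regression rejects | Terms only | 16 means, 8 df: power |
|---|---|---|---|---|---|
| 6,000 | 0.02 / 1.0 | 0.0256 | 5% | 5% | 98% |
| 6,000 | 0.02 / 0.9 | 0.0340 | 14% | 14% | 87% |
| 6,000 | 0.02 / 0.8 | 0.0407 | 21% | 22% | 73% |
| 6,000 | 0.05 / 0.8 | 0.0560 | 37% | 38% | 47% |
| 24,000 | 0.02 / 1.0 | 0.0128 | 5% | 5% | >99% |
| 24,000 | 0.02 / 0.9 | 0.0258 | 33% | 33% | 98% |
| 24,000 | 0.02 / 0.8 | 0.0341 | 46% | 46% | 87% |
| 24,000 | 0.05 / 0.8 | 0.0516 | 62% | 63% | 53% |

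The table assumes equal volumes and 2:2 starts. *Terms only* means hospital and period indicators with the ordinary regression variance (simulated). Analysis of the 16 hospital-period means with those terms and t on 8 df rejects a true null in about 5% of simulated trials in every row.

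**4. Not every cluster correction works.** With hospital and period terms fitted, a sandwich variance clustered on the four hospitals rejects a true null in about 30% of simulated trials uncorrected. With a 4/3 factor and 3 df it still rejects in about 12%.

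**The case against.** The strongest reply is that a balanced crossover already protects the estimate. With equal volumes and 2:2 starts, hospital and calendar effects cancel and the terms leave the sampling SD unchanged. If hospital-by-period variation is also absent, plain regression holds its 5% level. All of that stands. The plan also describes alternation between clusters, which suggests staggered starts, and a short model sentence does not forbid further terms. But neither equal volumes nor a 2:2 split is stated, and nothing in the plan rules out hospital-by-period variation.

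A second reply is that the inflated error rate is a variance problem that the terms do not touch. The *terms only* column confirms this, so the two parts must be specified together and their benefits kept apart.

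A reader might infer more in three ways that the documents do not support.

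- **A large loss of power in the planned analysis.** For 16 hospital-period means analysed without hospital terms, at an assumed hospital SD of 0.10 and SE 0.028, power is about 60%, against 96% with hospital and period terms. That is not the planned analysis. Patient-level regression with equal cells, 2:2 starts and no hospital-period variance keeps about 99% power there.
- **Systematic bias.** The trend shift has a random sign under randomization.
- **Covariates chosen by the 0.1 rule.** The plan does not say this, and analysts are masked. The gain from baseline covariates cannot be shown from the documents and may be negligible.

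**Conclusion.** The point holds. Run as written, the model ignores the cluster crossover structure, and the conditions under which that would be harmless are not secured by the plan. Under the assumed volumes and trend, the realised estimate moves by 8 to 19% of the target effect. Under the assumed correlations, the nominal 5% test rejects a true null in about 14 to 37% of trials (6,000 patients) or 33 to 62% (24,000).

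The direction of both effects follows from the design. Their size does not: SD, volumes, trend, ICC and CAC are all assumptions. At CAC 1 with equal volumes and 2:2 starts, the harm is nil. The 8 df result also relies on hospital-period errors being independent once hospital and period are fitted. The change is worth making before unmasking; the documents do not show that the trial's conclusion would differ.

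**What to change.** Replace the model sentence with one paragraph, fixed before unmasking, that specifies:

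- a linear model on log amount (the scale of the power paragraph) with condition, hospital indicators and period terms, and a rule for zero amounts, since eligibility is not limited to patients prescribed an opioid;
- a named small-sample method at hospital-period level, for example a hospital-period random effect with Kenward-Roger degrees of freedom, or analysis of the 16 hospital-period means on 16 − 8 = 8 df with 2:2 starts;
- the starting split, because period indicators cannot be fitted if all four hospitals started alike.

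Optional clarifications, with no shown gain: list any baseline covariates in advance, and state that the 0.1 check is descriptive.

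**Cost.** The terms and the variance method need no new data. In an analysis of 16 hospital-period means, residual df fall from 14 to 8 and the critical value rises from 2.145 to 2.306 (7.5%). If hospitals and periods truly do not differ, power for 0.12 falls from 97.8% to 96.2% at SE 0.028 (1.6 points). At SE 0.052 it falls from 58.1% to 53.3% (4.8 points); that SE is 0.5 × √(0.01 + 0.99/1500), assuming SD 1 and a within-hospital-period correlation of 0.01. Hospital terms alone (11 df) would cost less, with power of 97.3% and 56.4%, but would leave the calendar shift in place.

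### Does the log-scale effect measure break down because patients discharged with no opioid are eligible?

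*Combined protocol and SAP*

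**What the plan says.** The document has no numbered sections. Its opening paragraph sets eligibility: "Eligible secondary study subjects are postsurgical hospital inpatients who are hospitalized at least one night prior to discharge". On exclusions it says: "The exclusion criteria for eligible patients is being less than 18 years of age". Neither sentence asks for an opioid prescription at discharge.

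The analysis paragraph reads: "The analysis is conducted at the individual patient level using a modified intention-to-treat strategy". It continues: "The effect of the best practice alert on opioid prescription at discharge is evaluated using a linear regression model". No transformation is named there, and 'modified' is not explained.

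The closing paragraph on sample size and power works on a ratio scale. It claims more than 99% power "to detect a ratio of geometric means of 0.89 (ON/OFF) for the amount of prescribed opioids", restated as "a difference of -0.12 (ON – OFF) on the log-scale". The effect was reduced from 33.3% to 11.1% "to incorporate the average effect across all patients". The number available is given as feasible to "recruit 1,500 patients per cluster period across four hospitals for four time periods".

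**The concern.** A geometric mean is the exponential of a mean of logs, and the log of zero is undefined. If eligible patients include some discharged without an opioid, the quantity in the power paragraph cannot be computed over everyone the opening paragraph admits. Something must be done with the zeros, and the plan does not say what.

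The candidate rules are not interchangeable. Leaving out the zeros restricts the comparison to patients selected by a prescription written after the hospital-period was allocated, and it uses fewer patients than the plan counts. Adding a constant before taking logs keeps everyone, but the estimate, and far more so the power, then depends on the constant. The phrase about averaging over all patients could be read as including non-recipients or not. If the choice really were open and consequential, both the estimand and the power claim would be uncertain, and the rule could be settled after the data were seen.

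**Working it through.** **Inputs from the document:** ratio 0.89; log difference -0.12; alpha 0.05 (two-sided assumed); 1,500 patients per cluster period, four hospitals, four periods. The wording allows 1,500 × 4 × 4 = 24,000 patients or 1,500 × 4 = 6,000.

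**Inputs assumed, because the document gives none:** share of zeros 25%, the same in both conditions; positive amounts log-normal with log SD 0.8 and, where a constant is added, median 150; equal split between ON and OFF; no clustering.

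**1. The plan's own figures.** ln(0.89) = -0.1165 and ln(1 - 0.111) = -0.1177, both -0.12 when rounded. Also 0.111 / 0.333 = 1/3, so the averaging treats about a third of the averaged population as exposed to the alert. The power itself cannot be reproduced without an SD. The largest log SD compatible with 99% power is 0.1165 / [(1.960 + 2.326) × √(4/N)], which is 1.05 at N = 6,000 and 2.11 at N = 24,000. The claim is attainable.

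**2. Recipients only, 0.89 among recipients, 25% zeros.** SE = 0.8 × √(4/n).

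| n analysed | SE | 0.1165/SE | Power |
|---|---|---|---|
| 0.75 × 24,000 = 18,000 | 0.0119 | 9.77 | >99.9% |
| 0.75 × 6,000 = 4,500 | 0.0239 | 4.89 | 99.8% |

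At n = 4,500 the largest SD that still gives 99% is 0.91, against 1.05 with no zeros. At SD 1.0 and n = 4,500 power is 97.4%.

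**3. Recipients only, 0.89 already averaged over non-recipients.** The effect among recipients is then larger: exp(-0.1165 / 0.75) = 0.856 if averaged on the log scale, or 1 - 0.111/0.75 = 0.852 if averaged as percentages. With the first, 0.1554 / 0.0239 = 6.5 at n = 4,500, and power exceeds 99.9%.

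**4. All patients, constant c added before the log, 0.89 among recipients, 25% zeros.** SE = √[(V_OFF + V_ON)/(N/2)].

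| c | Log difference | SD (OFF) | Power, N = 24,000 | Power, N = 6,000 |
|---|---|---|---|---|
| 0.01 | -0.087 | 4.22 | 36% | 13% |
| 1 | -0.087 | 2.28 | 84% | 32% |
| 10 | -0.080 | 1.37 | 99.6% | 63% |

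The log difference barely moves with c; the SD does. The loss of power comes from the artificial distance between log c and the logs of real prescriptions. It describes a method that the plan does not mention.

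**5. All patients, ratio of arithmetic means, no constant.** Squared CV = exp(0.64)/0.75 - 1 = 1.53. SE of the log ratio = √(1.53 × 4/N) = 0.0160 at N = 24,000 and 0.0319 at N = 6,000. Power is >99.9% and 95%.

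**The case for a change.** The best case for a change is that the rule is not written and that it matters. Masking of investigators and analysts hides the ON/OFF label but does not fix the analysis set. Reading 'modified' as recipients only fits poorly with an effect averaged over all patients. The plan uses washouts to limit learning, which concedes that alerts could shape later prescribing, perhaps including whether an opioid is ordered at all. Even 5% zeros with log(x + 1) brings power to 89% at N = 6,000 on the inputs above.

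Part of this stands. The zero rule, the meaning of 'modified' and the population of the 0.89 are absent, and the log outcome itself is inferred from the power paragraph. Masking is a partial safeguard only.

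The step from missing wording to a wrong result does not stand. A log-scale regression cannot use undefined values, so the default is recipients only; an added constant would be a deliberate extra step. If the regression is instead on the raw amount, zeros enter without difficulty. The opening section says the alert appears when a provider attempts a dose above the optimum and suggests another dose, so the decision to prescribe ordinarily comes first. A cancelled order or a learned habit is possible, but nothing in the documents indicates either at a size that would bias the ratio.

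A yes/no opioid outcome or an all-patient mean ratio would add information and leave the primary result as it is. Declaring all discharges as the analysis set while limiting the ratio to recipients would itself need two separately defined populations.

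**Conclusion.** The concern identifies a real omission, but one that analysts fill in the ordinary way: log amount among patients who were prescribed an opioid. On that reading, with 25% zeros and log SD 0.8, power is 99.8% or above under either total and either reading of the 0.89, in line with the plan's claim. No change to the plan follows.

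This rests on an assumed share of zeros and SD, and on ignoring clustering, for which the document gives no correlation. The margin is not unlimited: with 4,500 recipients and SD 1.0, power is 97.4%, slightly short of the claim but of no consequence for the design. It also rests on the alert having little effect on who receives an opioid, which its trigger makes plausible but does not prove. The documents do not show that the figure of more than 99% is wrong, and the low powers in step 4 should not be quoted against the plan.
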